1. ABBREVIATIONS AND DEFINITIONS OF TERMS

AE	Adverse Event
ASA	Aspirin
bid	Twice Daily
BP	Blood Pressure
CBC	Complete Blood Count
CVC	Central Venous Catheters
DVT	Deep Vein Thrombosis
LMWH	Low Molecular Weight Heparin
od	Once Daily
po	by mouth
PE	Pulmonary Embolism
SAE	Serious Adverse Event
U/S	Ultrasound
ULN	Upper Limit of Normal
VTE	Venous Thromboembolic Event

2. STUDY SYNOPSIS

Title: A pilot study assessing the feasibility of a randomized controlled trial investigating primary thromboprophylaxis with rivaroxaban in patients with malignancy and central venous catheters (CVC)

Short Title: The TRIM-Line

Protocol Version: 28Feb2018 Version 1.1

Principal Investigators: [name] and [name]

Sponsor: OHRI

Study Centres:

The Ottawa Hospital, General Campus, Ottawa, ON
QEII Health Sciences Centre, Halifax, Nova Scotia
University of Alberta Hospital, Edmonton, Alberta

Timeline: February 2019-September2019

Purpose of Pilot Trial

To determine the feasibility of conducting a multicentre randomized open label-controlled trial evaluating the use of prophylactic dose rivaroxaban to prevent CVC associated venous thromboembolism(VTE) among cancer patients.

Purpose of Full Trial

The purpose of the full trial is to determine the efficacy and safety of prophylactic dose rivaroxaban to prevent CVC associated VTE among cancer patients.

Pilot Trial Endpoints

The primary feasibility outcome for the pilot study is the number of participants recruited per centre per month. We will obtain baseline details of the patient's type, location and treatment of cancer, comorbidities and medications. Secondary feasibility outcomes of the pilot study will include, consent rates, loss to follow up, adherence to therapy defining 80% or greater medication taken as having good adherence to study drug, proportion of screened patients who meet eligibility criteria.

We will document reasons for non-consent in order to assist recruitment for the larger multicentre trial.

Full Trial Endpoints

For the full multicentre trial the outcomes would be as follows: primary outcome symptomatic, radiographically confirmed VTE. Secondary outcomes include major and clinically relevant non-major bleeding (CRNMB), CVC life span, premature CVC removal, CVC lumen occlusion, CVC associated infection and death.

Design

This is a pilot study to be conducted at 3 Canadian Centres. The Ottawa Hospital, QEII Health Science Centre and University of Alberta Hospital. It is an open label randomized controlled trial.

Consenting participants, meeting eligibility criteria will be randomized at the time of enrollment to one of two groups.

Rivaroxaban 10mg po daily x 90 days

OR

Observation

Participants in the treatment arm will have study drug dispensed at Day 1 and take medication for 90 days. Follow up visits (in person or phone) will occur at Day 30 (+/- 3 days) and Day 90 (+/- 3 days) month and 3 months post enrollment. Overall, participants will be followed for 3 months. Adverse events will be collected for the first 90 days.

Number of participants

100

Inclusion and Exclusion Criteria

Inclusion criteria:

Patients 18 years of age or older with a new or existing diagnosis of cancer with a CVC inserted in the last 72 hours.

Exclusion criteria:

- 1) CVC in place for >72 hours
- 2) Patient requires anticoagulation for other indication
- 3) Concomitant use of dual antiplatelet therapy
- 4) Prior VTE
- 5) Major bleeding event in the last 6 weeks
- 6) Patient on concomitant medication with known interaction with rivaroxaban (eg. CYP3A4 inhibitor)
- 7) Pregnancy (documentation of use of effective contraception if sexually active or negative B- Hcg required)
- 8) Known renal failure, based on Creatinine clearance <30 mL/min (Cockcroft-Gault) (in the previous 3 months)*
- 9) Documented severe liver disease (eg. acute clinical hepatitis, chronic active hepatitis, cirrhosis or ALT >3ULN) (in the previous 3 months)*
- 10) Known thrombocytopenia < 50x 10⁹/L (in the previous 3 months)*
- 11) Allergy to rivaroxaban
- 12) Life expectancy <6 months
- 13) History of condition at increased bleeding risk including, but not limited to:
 - a) Major surgical procedure or trauma within 30 days before the randomization visit
 - b) Clinically significant gastrointestinal bleeding within 6 months before the randomization visit
 - c) History of intracranial, intraocular, spinal, or atraumatic intra-articular bleeding
 - d) Chronic hemorrhagic disorder
 - e) Known intracranial neoplasm, arteriovenous malformation, or aneurysm
 - f) Sustained uncontrolled hypertension: systolic blood pressure ≥180 mmHg or diastolic blood pressure ≥100 mmHg
- 14) Primary malignancy diagnosis of basal cell or squamous cell carcinoma of the skin or acute leukemia or myelodysplastic syndrome
- 15) Geographic inaccessibility
- 16) Refused or unable to obtain consent

* Baseline platelet count for inclusion/exclusion to be drawn within 2 weeks of enrolment.

SCHEDULE OF MANDATORY EVENTS

	Screening, Baseline and Randomization	Day 30 +/- 3 days	Day 90 +/- 3 days
Consent	✓		
Inclusion/Exclusion	✓		
Demographic	✓		
Randomization	✓		
Labs	✓		
History	✓		
Cancer Treatments	✓		
Dispense IP (Group 1)	✓		
Concomitant Medications	✓	✓	✓
IP Compliance		✓	✓
Outcome Information (Section 4.5)		✓	✓
Adverse Events		✓	✓

3. STUDY RATIONALE AND BACKGROUND

3.1 WHY IS A RANDOMIZED CONTROLLED TRIAL NEEDED?

Venous thromboembolism is a common but potentially fatal disease. A subtype of VTE, upper extremity deep vein thrombosis (UEDVT) accounts for approximately 4-11% of all VTE but unlike lower extremity deep vein thrombosis, UEDVT are poorly described and their risk and optimal treatment are not known (1). Many patients with cancer require insertion of a CVC in order to maintain venous access, administer chemotherapy, draw blood work and provide supportive care. UEDVT seems to be a frequent complication of CVC in this patient population receiving chemotherapy (3).

Pharmacologic thromboprophylaxis has been shown to be effective in reducing VTE in other high-risk populations such as hospitalized medical patients, those that have had hip or knee arthroplasty and in myeloma patients receiving immunomodulatory drugs (4, 5). While thromboprophylaxis is recommended in high risk cancer subgroups (e.g. hospitalized medically ill, post-major abdominal surgery, etc.) (6), it is not routinely recommended for the prevention of CVC associated VTE in outpatients with cancer. Previous comparative studies have not shown consistent clinical benefits (7-9).

3.2 WHY IS A CLINICAL TRIAL NEEDED NOW?

A recent meta-analysis by D'Ambrosio et al. suggests that prophylactic anticoagulation might reduce the risk of UEDVT in this high-risk patient population but notes heterogeneity in study results and highlights the need for a large prospective randomized trial in order to definitively answer this question (10).

Rivaroxaban is an oral factor Xa inhibitor with predictable pharmacokinetics that obviates the need for routine laboratory monitoring (11). The use of prophylactic rivaroxaban has been studied and proven efficacious to reduce VTE complications in other high-risk populations (post hip and knee arthroplasty, secondary prevention of VTE, etc.) (12). Furthermore, it is also currently under investigation in other high-risk cancer subgroups (CASSINI-Clinicaltrials.gov NCT02555878) (13). Until recently, the only options for pharmacologic prophylaxis were either a costly daily injection or warfarin which is difficult to manage safely in the context of cancer and chemotherapy. The convenience of an oral medication which does not require laboratory monitoring and its relatively short half-life are positive attributes which position rivaroxaban very well as an ideal agent for thromboprophylaxis of patients with cancer and a CVC (11). These qualities may potentially alter the risk versus benefit ratio of thromboprophylaxis use in favor of anticoagulation.

3.3 PRINCIPAL RESEARCH QUESTION

To assess the feasibility of conducting a multicentre randomized open label trial using Canadian centres and to assess the safety and efficacy of rivaroxaban to prevent CVC associated VTE among cancer patients.

3.4 WHY IS A PILOT RCT NEEDED BEFORE A FULL RCT CAN BE COMPLETED?

Recruitment of patients to a prophylaxis study which would add an additional medication and potentially further burden or complicate their care, may be challenging as patients may feel overwhelmed or be unwilling to accept the bleeding risks for a condition which they currently do not have. Thus, a pilot trial to assess feasibility of the larger RCT is needed first.

3.5 WHY IS AN OPEN-LABEL TRIAL DESIGN CHOSEN?

The current standard of care in most cancer patients is to not use outpatient thromboprophylaxis. Patients often receive thromboprophylaxis only when admitted to hospital or subject to additional risks. Not using a placebo tablet reduces study expense and complexity while improving patient acceptance and potentially enrollment into the trial. Since the primary endpoints in the larger planned multicentre study are objective, imaging confirmed thrombosis and bleeding outcomes and not expected to be adversely affected with an open label design.

4. TRIAL OBJECTIVES AND DESIGN

4.1 TRIAL PURPOSE

To determine the feasibility of conducting a multicentre randomized controlled trial comparing rivaroxaban at a prophylactic dose of 10mg daily versus standard of care (no prophylaxis) in patients with confirmed malignancy and insertion of a central venous catheter.

With the large sample size calculated to be required to demonstrate a difference using this intervention, confirmation of the ability to meet minimum recruitment rates is required prior to a launch of a large multicentre trial.

The overall goal of the full randomized trial is to demonstrate the safety and efficacy of using low dose rivaroxaban prophylaxis at preventing upper extremity venous thrombosis in patients with a diagnosis of malignancy and insertion of a central venous catheter.

4.2 TRIAL DESIGN

TRIM-Line is an open-label, randomized controlled feasibility pilot trial comparing rivaroxaban 10mg po daily vs standard of care (no treatment) in patients with active cancer and indwelling CVC. This will involve 3 centres, Ottawa as the coordinating centre, Halifax and Edmonton.

Cancer patients with insertion of CVC will be eligible.

While the primary outcome is feasibility based clinical data will be collected using the same methodology as the proposed full-sized trial. Should there be no major changes to the trial design based on the findings of this pilot study's feasibility data that would render the collected data inappropriate for inclusion, the clinical data collected during this trial will be included in the primary and secondary analysis for the full trial.

4.3 TRIAL INTERVENTION

Eligible and consenting patients will receive rivaroxaban 10 mg tablets to be taken once daily, starting within 72 hours of CVC placement. Randomization will occur in a 1:1 ratio via a central web-based randomization system.

The study drug will be continued until the CVC is removed, until one of the study outcomes is achieved, or until the end of the follow-up (90 Days +/- 3 days). Study medication will be held if the platelet count is $50 \times 10^9/L$ or less, the CrCl falls below 30mL/min, the patient experiences bleeding or the patient is required for treatment of cancer to start on a medication or chemotherapy which has a major interaction with rivaroxaban. All patients will be followed for 90 days (+/-3 days), unless they die or withdraw permission for follow up. At the end of the trial, VTE prophylaxis will be left to the discretion of the local investigator.

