4.10 PRODUCT LABELLING

Rivaroxaban will be purchased through the research pharmacy and relabeled for this trial according to the template below. Each participant in the treatment arm will be given a 93-day supply of study drug (according to the randomization scheme) at Day 1.

Product information for each of the study medications is listed in Appendix 4.

Rivaroxaban 10 mg Expiration: DD-MMM-YYYY Store at room temperature between +15°C and +25°C Lot # ----- Protocol : TRIM-Line Trial Sponsor: The Ottawa Hospital Research Institute, [name] Investigational drug -- to be used only by a qualified Investigator	Rivaroxaban 10 mg Expiration: JJ-MM-AAAA Conserver à l'air ambiant, entre +15°C et +25°C, Lot # ----- Nom du Protocole: TRIM-Line Trial Commanditaire: Institut de recherche de l'Hôpital d'Ottawa [name] Médicament expérimental -- à être utilisé seulement par un Investigateur qualifié
--	---

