4.14 PROPOSED FREQUENCY AND DURATION OF FOLLOW UP

In addition to the initial enrollment visit, patients that are enrolled will receive a telephone follow up at Day-30 +/- 3 days and an in person follow up at Day 90 +/- 3 days.

Post-enrollment follow up visits will include assessment and history for major and minor bleeding, CVC life span, premature CVC removal, CVC lumen occlusion, CVC associated infection and death and assessment of adherence to study drug. Patients will be followed for 90 days +/- 3 days.

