5 SAFETY

The adverse event reporting period will begin with the first dose of study medication and end on Day-90 +/- 3 days. Adverse events may be collected from participant report or by review of the clinical chart. Adverse events will be documented in the CRF.

Clinical investigators and ultimately the Qualified Investigator (QI) have the primary responsibility for adverse event identification, documentation, grading, assignment of attribution and reporting.

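### Section 4.3 makes a rivaroxaban hold mandatory at low platelets or low creatinine clearance, but nothing in the protocol requires either value to be obtained or reviewed after baseline

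*Protocol*

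**What the plan says.** Section 4.3 names four reasons to hold rivaroxaban. The first is introduced by "Study medication will be held if the platelet count is" 50 × 10⁹/L or less. The others are CrCl under 30 mL/min, bleeding, and the need to start a cancer treatment with a major interaction. Treatment runs until the catheter is removed, a study outcome occurs, or follow-up ends at Day 90 ± 3.

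The schedule of mandatory events in the synopsis ticks labs in the screening and baseline column only. Day 30 and Day 90 carry "Concomitant Medications", compliance, outcome information and adverse events. The only timing rule for a platelet count concerns entry: "Baseline platelet count for inclusion/exclusion to be drawn within 2 weeks of enrolment".

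Under section 4.14, participants "will receive a telephone follow up at Day-30 +/- 3 days" and are seen in person at Day 90. The content is given as follows: "Post-enrollment follow up visits will include assessment and history for major and minor bleeding", then catheter outcomes, infection, death and adherence. No laboratory item appears. The synopsis is looser and allows either contact to be in person or by phone.

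On supply, section 4.10 states: "Each participant in the treatment arm will be given a 93-day supply of study drug", dispensed at Day 1. On safety data, section 5 states: "Adverse events may be collected from participant report or by review of the clinical chart".

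**The concern.** The two laboratory triggers can be known only from a blood result. A mandatory safety rule for patients on an anticoagulant needs a required step that produces the result, or at least one that has the study team look for it. The protocol has neither after baseline. Because all the drug is dispensed at Day 1, no resupply visit prompts a check.

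At stake is participant safety and even application of the rule across three centres. Two sites that both follow the visit schedule could apply the hold quite differently, depending on how often their clinics draw blood and whether the research team reads the results. Section 4.2 says clinical data are collected by the full trial's methodology and may be included in it, so the gap would carry forward into a trial planned at 1892 patients (section 8.2).

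**Working it through.** The protocol states no figure to reproduce. The check sets the hold rule against the required assessments and then bounds the time involved.

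**Hold triggers against required checks**

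| Trigger (4.3) | Required at Day 30 | Required at Day 90 |
|---|---|---|
| Platelets 50 × 10⁹/L or less | none | none |
| CrCl under 30 mL/min | none | none |
| Bleeding | yes (4.14; outcome information) | yes |
| Interacting drug | yes (concomitant medications) | yes |

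Triggers without a required check: 4 − 2 = 2. Treatment ends at Day 90, so a check there comes too late to prompt a useful hold. The practical contrast is one scheduled check while drug continues for bleeding and interacting drugs, against none for platelets and CrCl.

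**Could other text supply the check?**

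- Section 3.1 says many cancer patients need a catheter to maintain venous access, "administer chemotherapy, draw blood work and provide supportive care". Routine results will therefore often exist. Section 4.4, however, asks only for a cancer diagnosis and a recent catheter. It does not require chemotherapy, and nothing requires the study team to read routine results.
- Section 5 permits chart review for adverse events but does not require it.
- Section 5.1 counts a laboratory value as an adverse event if, among other conditions, it has led to a change in study drug. That applies once someone has acted on a value. It orders no test.
- Section 7.1 gives a missing laboratory value at a specified visit as an example of a deviation. Baseline is the only visit with labs specified.
- Section 3.2 says rivaroxaban needs no routine laboratory monitoring. That is rationale about the drug and does not remove the thresholds that section 4.3 sets.
- The only on-study testing named is pregnancy testing (4.4).

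**Bounds**

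- Longest time on drug: 90 + 3 = 93 days, matching the 93-day supply. It is shorter if the catheter is removed or an outcome occurs.
- Participants allocated drug: 100 × 1/2 = about 50 under 1:1 randomization.
- Gap between the two contacts: shortest 87 − 33 = 54 days, longest 93 − 27 = 66 days. A review at Day 30 alone could leave up to 66 days of treatment uncovered, so the fix needs a repeating interval.

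**The case against.** The best defence is that the sponsor made a pragmatic choice: patients with cancer and a catheter usually have regular blood tests, the trial is open label so treating teams can know who is on rivaroxaban, and section 4.3 binds the site whenever a qualifying value is known. The primary outcome is recruitment per centre per month, which this point does not touch, and no planned analysis changes.

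Much of that stands. It narrows the affected group to participants with no routine results or with results the study team has not reviewed. It does not supply the missing step, since the protocol neither names routine care as the source nor asks anyone to look.

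Some stronger readings are tempting but are not supported:

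- A reader might infer that a site could keep a participant on drug with a qualifying result on file and still comply. It could not. The hold in 4.3 is unconditional, and section 7.2 lists dosing non-compliance as an example of a violation. The gap lies in obtaining and reviewing results.
- A reader might infer that a participant entering at exactly 50 × 10⁹/L must be held immediately. The entry count may be up to 2 weeks old, while the hold depends on the count during treatment and applies only to those allocated drug. The difference between the thresholds is a boundary mismatch only.
- A reader might cite section 5.1, under which non-serious cancer-related events are not recorded as adverse events. That governs recording and does not suspend the hold or affect detection.
- Day 30 should not be treated as telephone-only, because the synopsis also allows an in-person visit.

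**Conclusion.** The point holds and should be corrected. Two of the four hold triggers in section 4.3 have no required assessment or review after baseline, so their use depends on local routine care.

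The practical size is unknown. The protocol gives neither the share of participants without routine bloods nor the rate at which platelets or CrCl fall to the thresholds. The figures of 93 days and about 50 participants are upper bounds. A reader might take them as the expected exposure, but the documents do not support that, because routine testing will shorten the gap for many.

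The conclusion rests on the protocol text alone. Section 6.1 refers to a resource manual for the detailed monitoring plan. That manual is not shown, and nothing in the protocol says it schedules patient blood tests.

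**What to change.** 1. In the schedule of mandatory events and section 4.14, require sites, for participants on rivaroxaban, to review routine-care platelet and creatinine results (CrCl by Cockcroft-Gault) at Day 30 and at a set interval until treatment ends, for example monthly or with each chemotherapy cycle.
2. Require sites to apply the 4.3 hold on that review and to record the triggering value and the hold dates in the CRF.
3. As an option, require a blood draw when an interval has passed with no routine result. Without this, participants who have no routine bloods remain unchecked.
4. As a minor alignment, change the platelet exclusion in the synopsis and section 4.4 from below 50 to 50 × 10⁹/L or less, to match the hold threshold.

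The cost is a few wording changes, a CRF entry and some chart-review time, repeated at each interval. The optional draw adds a further small cost and, where Day 30 is done by telephone, an extra attendance. Analysis and sample size are unaffected.

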4.4 ELIGIBILITY

Inclusion and Exclusion Criteria

Inclusion criteria:

Patients 18 years of age or older with a new or existing diagnosis of cancer with a CVC inserted in the last 72 hours.

Exclusion criteria:

- 17) CVC in place for >72 hours
- 18) Patient requires anticoagulation for other indication
- 19) Concomitant use of dual antiplatelet therapy
- 20) Prior VTE
- 21) Major bleeding event in the last 6 weeks
- 22) Patient on concomitant medication with known interaction with rivaroxaban (eg. CYP3A4 inhibitor)
- 23) Pregnancy (documentation of use of effective contraception if sexually active or negative B- Hcg required) **
- 24) Known renal failure, based on Creatinine clearance <30 mL/min (Cockcroft-Gault) (in the previous 3 months)*
- 25) Documented severe liver disease (eg. acute clinical hepatitis, chronic active hepatitis, cirrhosis or ALT >3ULN) (in the previous 3 months)*
- 26) Known thrombocytopenia < 50x 10⁹/L (in the previous 3 months)*
- 27) Allergy to rivaroxaban
- 28) Life expectancy <6 months
- 29) History of condition at increased bleeding risk including, but not limited to:
 - g) Major surgical procedure or trauma within 30 days before the randomization visit
 - h) Clinically significant gastrointestinal bleeding within 6 months before the randomization visit
 - i) History of intracranial, intraocular, spinal, or atraumatic intra-articular bleeding
 - j) Chronic hemorrhagic disorder
 - k) Known intracranial neoplasm, arteriovenous malformation, or aneurysm
 - l) Sustained uncontrolled hypertension: systolic blood pressure ≥180 mmHg or diastolic blood pressure ≥100 mmHg
- 30) Primary malignancy diagnosis of basal cell or squamous cell carcinoma of the skin or acute leukemia or myelodysplastic syndrome
- 31) Geographic inaccessibility
- 32) Refused or unable to obtain consent

** Women of child-bearing potential will be asked to have a baseline pregnancy test done. She must agree to ongoing pregnancy testing during the study, and after end of study therapy. This applies even if the subject practices true abstinence from heterosexual contact. She must either commit to true abstinence from heterosexual contact (which must be reviewed at subsequent study visits and source documented) or agree to use and be able to comply with highly effective

contraception without interruption, during the study therapy (including dose interruptions), and for 30 days after discontinuation of study therapy.

Male subjects must practice true abstinence (reviewed at subsequent study visits) or agree to use a condom during sexual contact with a pregnant female or a female of childbearing potential while participating in the study, during dose interruptions and for at least 30 days following investigational product discontinuation, even if he has undergone a successful vasectomy.

Acceptable methods of contraception include: combined (estrogen and progestogen containing) hormonal contraception: oral; Intravaginal; transdermal; progestogen-only hormonal contraception associated with inhibition of ovulation: oral; Injectable hormonal contraception; Implantable hormonal contraception; placement of an intrauterine device; placement of an intrauterine hormone-releasing system; bilateral tubal occlusion; vasectomized partner.

